- 1050 The following is a summary of the definition of the outcome measures. The Statistical Analysis Plan details the analysis approach for all outcomes. 1051
- 1052

1053 7.1. PRIMARY OUTCOME MEASURES

1054 7.1.1. SAFETY MEASURES

- 1055 The occurrence of the following adverse events at any time during the 18 months of follow-up in 1056 the recipient eye will serve as the primary safety events of interest:
- 1057
- 1058 1. Ocular infection (defined as endophthalmitis or microbial keratitis [bacterial, fungal, 1059 parasitic])
- 1060 2. Corneal perforation
- 1061 3. Graft detachment \geq 50%
- 1062
- 1063 In addition to the primary safety events, all adverse events (systemic and ocular in donor and 1064 recipient eyes) will be captured. The severity of each adverse event and the relationship of the
- 1065 event to the cell therapy procedure will be assessed by an independent Medical Monitor(s)
- 1066 (MM). The independent Medical Monitor's (see Section 9.3) coding of the adverse event and
- 1067 designation of severity and relatedness to treatment will serve as final to use for adverse event
- 1068 reporting and safety outcome analysis.
- 1069

1070 7.1.2. FEASIBILITY MEASURES

- 1071 Manufacturing feasibility will be evaluated for each biopsy attempt. At least one CALEC
- 1072 construct will be attempted to be manufactured from each biopsy, as detailed in the MOP. Each
- 1073 attempted construct will undergo Quality Control (QC) testing to determine product conformity to
- 1074 CMCF release criteria per MOP, which includes assessments of cell growth, cell viability, and
- 1075 culture contamination. If all of these QC release criteria are met for at least one CALEC
- 1076 construct, the biopsy attempt is considered a feasibility success.
- 1077
- 1078 In the event that a construct met all QC release criteria, but surgery was not performed for a reason unrelated to the development of construct for transplant, the case would still be
- 1079 1080 considered a feasibility success for the biopsy attempt.
- 1081
- 1082 Up to two biopsy attempts of a single participant may be performed according to Section 5. Feasibility analysis will explore both the number of biopsies per participant and the number of 1083
- 1084 construct attempts per biopsy, and whether those construct attempts met QC release criteria.

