- 1085 Each of the individual QC testing and acceptance criteria will be documented to further describe 1086 constructs that did not meet the criteria for release. 1087

1088 **7.2. SECONDARY OUTCOME MEASURES**

- 1089 Efficacy Measures: The primary efficacy outcome will be a binary "Complete Success" of the 1090 graft, as defined below. Secondarily, "Partial Success" will also be considered according to a 3 1091 category outcome defined below.
- 1092 1. "Complete Success" will be defined as *improvement* in corneal surface integrity 1093
 - 2. "Partial Success" will be defined as
 - a. No improvement in corneal surface integrity and
- 1095 b. Improvement in either 1096
 - i. Extent of corneal vascularization or
 - ii. Participant symptomatology
 - 3. Otherwise, not a success
- 1098 1099

1097

- 1100 Improvement in each area is defined as follows, where changes are measured relative to 1101 the Baseline visit:
- 1102
- Corneal surface integrity • 1103
 - o If epithelial defect surface area (based on clinical assessment) at the Baseline visit is > 0 mm², then *improvement* will be defined as:
 - Decrease in epithelial defect surface area (based on clinical assessment by an independent investigator, not the treating surgeon, as described in the MOP) by \geq 75%
 - If epithelial defect surface area (based on clinical assessment) at the Baseline 0
 - visit is = 0 mm^2 , then *improvement* will be defined as:
 - Epithelial defect surface area of 0 mm² and
 - Decrease in corneal surface staining (based on clinical assessment by an independent investigator, not the treating surgeon, using NEI grading scale) by $\geq 50\%$
 - Extent of corneal vascularization •
 - o Decrease in neovascular area (based on digital slit lamp photographs, using mathematical software to calculate as described in the MOP) by $\geq 25\%$
 - Participant symptomatology
 - Decrease in Ocular Surface Disease Index (OSDI) score by ≥25% or 0
 - Decrease in Symptom Assessment in Dry Eye (SANDE) score by ≥25% 0

1121 The primary efficacy time points will be at 3 months (to assess early success), as well as 12 and 1122 18 months (to assess late success). Efficacy outcomes at all interim post-3 month time points will also be evaluated secondarily. The pattern of efficacy outcomes for an eye at these and all 1123 1124 interim time points 3 months and later will be evaluated secondarily to assess the degree of 1125 stability of each level of success over time. 1126

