2.0 Study Outcomes

20 21

Excerpt from Protocol Section 7:

22 23

PRIMARY OUTCOME MEASURES
SAFETY MEASURES

Safety will be assessed in both the CALEC and CLAU groups. The occurrence of the following adverse events at any time during the 18 months of follow-up in the recipient eye will serve as the **primary safety** events of interest:

- 1. Ocular infection (defined as endophthalmitis or microbial keratitis [bacterial, fungal, parasitic])
- 2. Corneal perforation
- 3. Graft detachment ≥50%

In addition to the primary safety events, all adverse events (systemic and ocular in donor and recipient eyes) will be captured. The severity of each adverse event and the relationship of the event to the cell therapy procedure will be assessed by an independent Medical Monitor(s) (MM). The independent Medical Monitor's (see Section 9.3) coding of the adverse event and designation of severity and relatedness to treatment will serve as final to use for adverse event reporting and safety outcome analysis.

FEASIBILITY MEASURES

Manufacturing feasibility will be evaluated in the CALEC group, for each biopsy attempt. At least one CALEC construct will be attempted to be manufactured from each biopsy, as detailed in the MOP. Each attempted construct will undergo Quality Control (QC) testing to determine product conformity to CMCF release criteria per MOP, which includes assessments of cell growth, cell viability, and culture contamination. If all of these QC release criteria are met for at least one CALEC construct, the biopsy attempt is considered a feasibility success.

In the event that a construct met all QC release criteria, but surgery was not performed for a reason unrelated to the development of construct for transplant, the case would still be considered a feasibility success for the biopsy attempt.

Up to two biopsy attempts of a single participant may be performed according to Section 5. Feasibility analysis will explore both the number of biopsies per participant and the number of construct attempts per biopsy, and whether those construct attempts met QC release criteria. Each of the individual QC testing and acceptance criteria will be documented to further describe constructs that did not meet the criteria for release.

SECONDARY OUTCOME MEASURES

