Efficacy Measures: Efficacy will be assessed in both CALEC and CLAU groups. The primary efficacy outcome will be a binary "Complete Success" of the graft, as defined below. Secondarily, "Partial Success" will also be considered according to a 3 category outcome defined below.

- 1. "Complete Success" will be defined as improvement in corneal surface integrity
- 2. "Partial Success" will be defined as
 - a. No improvement in corneal surface integrity and
 - b. Improvement in either
 - i. Extent of corneal vascularization or
 - ii. Participant symptomatology
- 3. Otherwise, not a success

Improvement in each area is defined as follows, where changes are measured relative to the Baseline visit:

- Corneal surface integrity
 - o Decrease in epithelial defect surface area (based on clinical assessment by an independent investigator, not the treating surgeon, as described in the MOP) by ≥75% or
 - o Decrease in corneal surface staining (based on clinical assessment by an independent investigator, not the treating surgeon, using NEI grading scale) by ≥50%
- Extent of corneal vascularization
 - Decrease in neovascular area (based on digital slit lamp photographs, using mathematical software to calculate as described in the MOP) by ≥25%
- Participant symptomatology

- o Decrease in Ocular Surface Disease Index (OSDI) score by ≥25% or
- o Decrease in Symptom Assessment in Dry Eye (SANDE) score by ≥25%

The primary efficacy time points will be at 3 months (to assess early success), as well as 12 and 18 months (to assess late success). Efficacy outcomes at all interim post-3 month time points will also be evaluated secondarily.

OTHER OUTCOME MEASURES

In addition to the primary and secondary outcome measures defined above, distribution of data and summary statistics will be evaluated on the following in both groups at each time point where relevant data are collected: IOP, impression cytology, corneal opacification, visual acuity. All reported adverse events will also be tabulated in both groups.

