 - b. Adverse Events designated by the DSMC as requiring expedited reporting (defined in the DSMC Charter) will be tabulated. The Charter describes in detail whether the events of interest are related to the donor or recipient eye and the time frame for classifying an event as an expedited event. CALEC Group Phase A, CALEC Group Phase B, and CLAU Group will be tabulated separately.
- Feasibility Analysis
- Feasibility will be assessed in the CALEC group only, using patients from both Phase A and Phase B. Each biopsy attempt will be classified as a "feasibility success" if it produced at least one construct that met all of the Quality Control (QC) release criteria in the CALEC Manual of Procedures. Secondarily, the number of biopsy attempts for each patient, as well as the QC results of all construct attempts for each biopsy, will be explored.
- The following feasibility analyses will be performed.

- 1. **Primary Feasibility Analysis:** On a biopsy level (denominator is the total number of biopsies performed)
 - o Number and percentage of biopsy attempts resulting in a feasibility success
- 2. Secondary Feasibility Analysis: On a patient level (denominator is all patients for whom at least 1 biopsy was performed)
 - o Categorize the number and percentage of patients for whom the biopsy (1) produced a feasibility success on the first biopsy attempt, (2) failed first attempt but produced a success on a second biopsy attempt, (3) failed 2 attempts, or (4) failed first attempt and a second was not attempted
- 3. Secondary Feasibility Analysis: On a construct level
 - o Categorize the number and percentage of constructs that met all QC release criteria
 - The QC criteria that failed and the data for each individual QC release criteria will also be explored.

Efficacy Analysis

The following efficacy analyses will be performed.

- 1. Primary Efficacy Analysis (within-CALEC evaluation of primary efficacy outcome):
 - a. The primary efficacy outcome measure is the binary outcome "Complete Success" of the graft versus not (as defined in the Protocol). This measure will be evaluated at each of the following three time points: 3, 12 and 18 months. The number and percentage of participants meeting the "Complete Success" criteria will be tabulated at each of these time points.
 - i. Evaluate in CALEC Group Phase A and Phase B participants combined. Only participants who completed transplant will be included.

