 - ii. For all participants with missing data on the primary efficacy outcome at any of the time points, multiple imputation will be performed for the "Complete Success" status using logistic regression.
- 2. Primary Efficacy Analysis (CALEC versus CLAU comparison of primary efficacy outcome):
 - a. The primary efficacy outcome measure is the binary outcome "Complete Success" of the graft versus not (as defined in the Protocol). This measure will be evaluated at each of the following three time points: 3, 12 and 18 months. The number and percentage of participants meeting the "Complete Success" criteria will be tabulated at each of these time points.
 - i. Evaluate within each treatment group, in Phase B participants only. All participants who were randomized will be included regardless of whether transplant was completed. Phase B participants who discontinued prior to randomization will not be included.
 - ii. Participants who were randomized but did not receive a transplant will be included in the analysis as a failure.
 - iii. For all participants with missing data on the primary efficacy outcome at any of the time points, multiple imputation will be performed for the "Complete Success" status using logistic regression.
 - b. The two treatment groups will also be compared by computing the differences in percentages meeting "Complete Success" and 95% confidence intervals around those differences, at each time point.
 - c. As a secondary analysis, a longitudinal model of the percentage of patients with "Complete Success" at each protocol-specified examination time (including visits in-between 3, 12 and 18

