240 241 group interactions. 242 243 244 245 246 247 248 participants who completed transplant will be included. 249 ii. Missing data will not be imputed for this secondary analysis. 250 251 252 253 254 255 256 257 258 259 260 analysis as failures. 261 iii. Missing data will not be imputed for this secondary analysis. 262 263 264 265 266 267 268 269 where the data are collected. 270 271 272 continuous variable 273 274 assessment*) ≥75% 275 276 continuous variable 277 278 scale) by ≥50% 279 280 variable 281 282 7) Percentage change from baseline in OSDI score - continuous variable 283 8) Proportion of participants with decrease in OSDI score by ≥25% 284 9) Percentage change from baseline in SANDE score - continuous variable 285 10) Proportion of participants with decrease in SANDE score by ≥25% 286 * Epithelial defect surface area based on photographic images will also be evaluated. 287 288 289 290 percentages. 291 292

month) will be applied using a mixed effects logistic regression, including time by treatment

3. Secondary Efficacy Analysis (within-CALEC group evaluation of secondary efficacy outcome):

- a. The secondary efficacy outcome measure is the 3 level categorical outcome ("Complete Success", "Partial Success", "Not a Success", as defined in the Protocol). This measure will be evaluated at each of the following three time points: 3, 12 and 18 months. The number and percent of participants in each outcome category will be tabulated at each of these time points.
 - i. Evaluate in CALEC Group Phase A and Phase B participants combined. Only

4. Secondary Efficacy Analysis (CALEC versus CLAU comparison of secondary efficacy outcome):

- a. The secondary efficacy outcome measure is the 3 level categorical outcome ("Complete Success", "Partial Success", "Not a Success", as defined in the Protocol). This measure will be evaluated at each of the following three time points: 3, 12 and 18 months. The number and percent of participants in each outcome category will be tabulated at each of these time points.
 - i. Evaluate within each treatment group, in Phase B participants only. All participants who were randomized will be included regardless of whether transplant was completed. Phase B participants who discontinued prior to randomization will not be included.
 - ii. Participants who are randomized but do not receive a transplant will be included in the

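### The SAP prints a looser rule for Complete Success than the Protocol rule its own analysis section cites; the two disagree when staining halves but a defect persists, grows or appears

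*SAP*

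**What the plan says.** SAP 2.0 is headed "Excerpt from Protocol Section 7". Under corneal surface integrity it gives two limbs. The first is a fall in epithelial defect area, assessed by an "independent investigator, not the treating surgeon, as described in the MOP) by ≥75% or"; the second, joined by that last word, is a fall in NEI staining of at least 50%. Either is enough, and baseline defect status plays no part. Improvement in corneal surface integrity is Complete Success.

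Protocol 7.2 branches on the baseline visit. The first branch opens "If epithelial defect surface area (based on clinical assessment) at the Baseline visit is > 0" mm² and accepts only a fall in defect area of at least 75%. The second, for a baseline area of 0 mm², requires "Epithelial defect surface area of 0" mm² at follow-up together with a staining fall of at least 50%.

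On which text governs:

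- Protocol 7 introduces its content with "The following is a summary of the definition of the outcome measures" and leaves the analysis approach to the SAP.
- SAP 5.0 describes the primary efficacy measure as Complete Success "of the graft versus not (as defined in the Protocol"). It makes the same reference for the three-category measure ("The secondary efficacy outcome measure is the 3 level categorical outcome").
- SAP 3.0 instead points back to the definition printed earlier in the SAP, which is the *or* rule.

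**The concern.** A programmer working from SAP 2.0 and one working from Protocol 7.2 would classify some eyes differently on the primary efficacy outcome. Under the SAP text, an eye whose defect has not healed, has enlarged or is new counts as a Complete Success on staining alone. Under the Protocol it does not.

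Both baseline branches can occur. Eligibility (Protocol 5.1) rests on fibrovascular pannus and does not require an epithelial defect. Protocol 15.1 also foresees CALEC recipients whose defect is unresolved after 12 months.

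The three-category outcome inherits the mismatch: a discordant eye that the Protocol calls Partial Success or not a success becomes Complete Success under SAP 2.0.

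The study is open label and the assessors are unmasked (Protocol 5.5). Two written rules leave room to choose between them after the data are seen. The efficacy results are meant to help size later trials (Protocol 2.3, SAP 4.0), so the definition behind the rate matters beyond this study.

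**Working it through.** No figure in the plan depends on this definition, so there is none to reproduce. The check compares the two rules.

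**Notation.** Defect area is b at baseline and f at follow-up (mm²). NEI staining is s0 at baseline and s1 at follow-up (0 to 15, Protocol 6.6.4.2). A percentage fall from a baseline of zero is undefined and is treated as not met.

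- SAP 2.0: success if (b − f)/b ≥ 0.75 **or** (s0 − s1)/s0 ≥ 0.50.
- Protocol 7.2, b > 0: success if (b − f)/b ≥ 0.75.
- Protocol 7.2, b = 0: success if f = 0 **and** (s0 − s1)/s0 ≥ 0.50.

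**Step 1: Protocol success implies SAP success.** The b > 0 branch is the first SAP limb. The b = 0 branch contains the second SAP limb.

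**Step 2: where the reverse fails.** Staining must fall by at least 50%, and either b > 0 with area reduced by less than 75% (including unchanged or larger), or b = 0 with f > 0. Eyes with no defect at either visit are classified alike.

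**Step 3: enumeration.** Integer areas 0 to 40 mm² and NEI scores 0 to 15 at each visit give 41² × 16² = 430,336 combinations. None is a success under the Protocol only. All SAP-only combinations fall in the Step 2 categories. This shows logic, not frequency.

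**Step 4: worked eyes.**

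| Defect (mm²) | NEI | Staining fall | SAP 2.0 | Protocol 7.2 |
|---|---|---|---|---|
| 20 to 20 | 15 to 7 | 8/15 = 53.3% | success | not |
| 0 to 6 | 12 to 6 | 6/12 = 50% | success | not |
| 4 to 6 | 10 to 3 | 7/10 = 70% | success | not |
| 4 to 1 (75% fall) | 10 to 3 | 70% | success | success |
| 0 to 0 | 10 to 3 | 70% | success | success |

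**Step 5: size per eye.** Each discordant eye shifts the observed rate by 100/n points. At the Protocol 5.5 cap, n = 17, this is 1/17 = 5.9 points. As an illustration with an assumed number of discordant eyes, let SAP 2.0 give 13/17, which lies within the 70–80% expected in SAP 3.0 (exact 95% intervals):

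| Discordant eyes (assumed) | Protocol 7.2 rate | 95% interval |
|---|---|---|
| 0 | 13/17 = 76.5% | 50.1–93.2 |
| 1 | 12/17 = 70.6% | 44.0–89.7 |
| 2 | 11/17 = 64.7% | 38.3–85.8 |
| 3 | 10/17 = 58.8% | 32.9–81.6 |

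**Step 6: after imputation the direction is not fixed.** SAP 5.0 says "For all participants with missing data on the primary efficacy outcome at any of the time points, multiple imputation will be performed" by logistic regression, with no covariates named. Take a hypothetical 17 eyes with 3-month status as predictor. Under Protocol 7.2, 12 succeed at 3 months; 10 of these are seen at 18 months, 9 succeed, and 2 are missing. The other 5 all fail at 18 months. The expected 18-month rate is (9 + 2 × 9/10)/17 = 10.8/17 = 63.5%. If the *or* rule turns 2 of those 5 into successes at 3 months only, it is (9 + 2 × 9/12)/17 = 10.5/17 = 61.8%. The looser rule can therefore lower an imputed estimate.

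**The case against.** The strongest reply is that the documents already indicate which rule applies. SAP 5.0 defers to the Protocol, Protocol 7 holds the definitions, and SAP 2.0 presents itself as a copy. On that reading the SAP text is a stale excerpt and a careful analyst would use Protocol 7.2. This has force and decides the direction of the fix. It does not remove the printed rule: SAP 5.0 names no Protocol section or version, and SAP 3.0 relies on the SAP's own text.

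The effect may also be nil. Defect area and staining come from the same fluorescein examination, and nothing in the documents shows how often staining halves while a defect remains. The 5.9 points is only the step per eye at n = 17. This stands.

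Protocol 15 is limited support. Its second-transplant criteria are independent of success status, at most three participants may be regrafted, and primary efficacy data stop before the second biopsy (15.7.3). It shows that unresolved defects were foreseen, not that they coincide with a large staining fall.

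Finally, SAP 5.0 also reports the 75% defect criterion and the 50% staining criterion separately at each time point. That helps a reader but does not show which eyes met only one.

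**Conclusion.** The concern holds. SAP 2.0 does not reproduce the current Protocol 7.2 and is the looser rule for observed status. The observed Complete Success rate under the SAP text is the same or higher, by 100/n points per discordant eye (5.9 at n = 17). The number of such eyes is unknown, and the direction is not guaranteed once missing status is imputed. The result assumes that a percentage fall from a zero baseline counts as not met.

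The mismatch probably arose because the SAP text predates the current Protocol. This is inferred from the CLAU randomization still in SAP 1.0 and 4.0, which Protocol 12 says was dropped at v5.0. The within-CALEC efficacy analyses remain current, so the conflict is live.

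It should be fixed before analysis. It does not threaten the primary objectives: efficacy is secondary and exploratory, and no safety, feasibility or sample-size figure uses this definition.

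**What to change.** Replace the corneal surface integrity text in SAP 2.0 with the baseline-dependent rule of Protocol 7.2. State before analysis that this rule governs the binary and three-category outcomes at all time points, and any Complete Success status used in the imputation model. As optional housekeeping, have SAP 3.0 refer to the Protocol definition rather than to the SAP's own text.

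The cost is one text replacement and one programming rule, with no new data. The downside is that the reported success rate may be lower than under the SAP wording.

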3.0 Study Hypotheses

Safety: We expect the probability of seeing at least one primary safety event in the recipient eye (infection, perforation, or detachment) in the CALEC group will be close to 5% (based on current literature, see separate document *Summary of Previous Literature*).

Feasibility: We expect 5-10% or fewer CALEC constructs will fail to meet the feasibility criteria prior to transplantation as defined in the protocol (based on preliminary experiments at the Connell and O'Reilly Families Cell Manipulation Core Facility, which will manufacture the CALEC construct for this study).

Efficacy: We hypothesize that the proportions with early and late graft success as defined above in the CALEC group will be similar to that of the CLAU group. Based on current literature (see separate document *Summary of Previous Literature*) we expect the percentage to be between 70-80% in each group

